8 SAFETY ANALYSIS

8.1 Adverse Events

The Medical Dictionary for Regulatory Activities (MedDRA) dictionary version 18.0 or higher will be used for coding adverse events (AEs). Each verbatim term will be mapped to a preferred term and system organ class (SOC).

An AE (classified by system organ class and preferred term) that occurs during the treatment period will be counted as a treatment-emergent AE (TEAE) either if it is not present at Baseline or if it is present at Baseline but increased in severity during the treatment period or follow up period.

The number (percentage) of subjects reporting TEAEs for each preferred term will be tabulated by system-organ class, by system-organ class and severity, and by system-organ class and relationship to study drug. If more than one event occurred with the same preferred term for the same subject, the subject will be counted only once for that preferred term using the most severe or related occurrence for the summary by severity, or relationship to study drug, respectively.

Summaries of serious adverse events (SAEs) and AEs leading to study discontinuation will also be provided by system organ class and preferred term. Listings of SAEs and AEs leading to treatment or study discontinuation will also be provided.

In the presentation, SOC and preferred term will be sorted in alphabetical order.

All AEs captured in the database will be listed in by-subject data listings; however, only TEAEs will be summarized.

MedDRA version will be footnoted in both tables and data listings.

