#### Clinical evaluation time points:

- Assessment of safety (adverse events and PT/INR testing) Days 1, 2, 3, 7 and 14
- Early clinical efficacy evaluation at 48 to 72 hours from start of oritavancin administration
- Post-therapy efficacy evaluation at Day 7

**Statistical Methods:** Approximately 25 subjects on chronic warfarin therapy will be enrolled (ITT population). An additional group of 15 ABSSSI patients, who are not on chronic warfarin therapy, will also be enrolled.

**Sample size:** The sample size of 25 subjects is chosen based on feasibility and clinical judgment to provide adequate safety information on the administration of oritavancin to subjects with an ABSSSI who are on chronic warfarin. An additional group of 15 ABSSSI patients who are not on chronic warfarin therapy was added to obtain information regarding potential for antibody production related to oritavancin administration.

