# 6. SEQUENCE OF PROCEDURES

A summary of clinical assessments and procedures is provided before the contents in Schedule of Events.

This study consists of four periods: Screening, Pre-Dose, Treatment, and Follow-up. The maximum duration of a patient's participation in this study is approximately 14 days post first administration of oritavancin.

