#### 6.4. TREATMENT PERIOD

The enrollment process will be initiated only after confirmation of a subject's eligibility. Each successive subject will be assigned a unique subject identification number.

If a subject is found to be ineligible after signing the informed consent, but prior to dosing, he or she will be considered a screen failure, the subject will not be enrolled, and oritavancin will not be administered.

## 6.4.1. Day 1

Ideally, treatment should be initiated within 4 to 6 hours after the patient is first seen on Day 1.

- Administer oritavancin as a single IV infusion of 1200 mg over 3 hours
- Vital signs (blood pressure, heart rate, respiratory rate and temperature)
- Collection of concomitant medication information.
- Assessment of AEs and SAEs
- Collect blood sample for Drug Dependent Antibody Ex Vivo Study (immediately after the completion of the oritavancin infusion).

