## 6.5. FOLLOW UP

#### 6.5.1. Day 2

 Collect blood sample for PT/INR coagulation test (window: 18-36 hours after the start of the oritavancin infusion).

## 6.5.2. Day 3

- Vital signs (blood pressure, heart rate, respiratory rate and temperature)
- Assessment of early clinical cure at 48-72 hours after start of infusion of Oritavancin
- Assessment of AEs and SAEs
- Collect blood specimens for immunoglobulin panel, oritavancin antibody assay, PT/INR coagulation test, direct and indirect Coombs test
- Collection of concomitant medication information

# 6.5.3. Day 7

- Obtain vital sign measurements (blood pressure, heart rate, respiratory rate and temperature)
- Collect blood specimens for hematology, serum chemistry, immunoglobulin panel, oritavancin antibody assay, PT/INR coagulation test, direct and indirect Coombs test
- A urine pregnancy test will be performed for female subjects of childbearing potential. This test may be omitted for females >2 years postmenopausal or surgically sterile.
- Assessment of clinical cure
- Collection of concomitant medication information
- Assessment of AEs and SAEs

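### As written, the TEAE rule counts a new adverse event only if it starts on Day 1, so new events on Days 2–14 would be left out of the AE tables

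*SAP*

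**What the plan says.** SAP 8.1 sets the rule. Its first branch covers new events: an AE "that occurs during the treatment period will be counted as a treatment-emergent AE (TEAE) either if it is not present at Baseline". The second branch covers conditions the subject already had, and only here does follow-up appear; such an AE counts "if it is present at Baseline but increased in severity during the treatment period or follow up period". Protocol 10.3.3.1 uses the same sentence. SAP 8.1 then limits what reaches the tables: "All AEs captured in the database will be listed in by-subject data listings; however, only TEAEs will be summarized". It also promises SAE and discontinuation tables: "Summaries of serious adverse events (SAEs) and AEs leading to study discontinuation will also be provided by system organ class and preferred term". It does not say which time window those tables use.

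The term treatment period has a meaning in the protocol. Section 6 states: "This study consists of four periods: Screening, Pre-Dose, Treatment, and Follow-up". Section 6.4, headed as the treatment period, has one subsection, Day 1, whose dosing step is "Administer oritavancin as a single IV infusion of 1200 mg over 3 hours". Section 6.5, Follow Up, opens with Day 2 ("window: 18-36 hours after the start of the oritavancin infusion") and continues with Days 3, 7 and 14. The protocol's Table 1 uses the same column headings. Neither document defines the term in any other way or gives an end date for TEAEs.

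AEs are collected from consent through 14 days after oritavancin (Protocol 3.4, SAP 3.3). Their incidence is a named component of the primary endpoint (SAP 2.3.1).

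**The concern.** Treatment is a single infusion, so the treatment period as the protocol lays it out is one day. A programmer who applies the TEAE sentence with the protocol's own periods would flag a new AE on Day 1 and reject a new AE on Day 2 or later. Because only TEAEs are tabulated, the AE incidence tables would cover one day while the listings in the same report cover fourteen.

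The lost days matter for this question. Protocol 1.3 says the study is meant to describe the size and duration of any change in warfarin dosing or any clinically important consequence. Protocol 1.2.4 says oritavancin may raise warfarin concentrations and calls for close monitoring for bleeding. The terminal half-life in Protocol Table 2 is 245 h, or 245/24 = 10.2 days, so exposure continues well into Follow-up.

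**Working it through.** There is no stated figure to reproduce: the sample size rests on feasibility and clinical judgment. The check is of the text, followed by an illustration of size.

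**1. Applying the rule to each type of event**

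| Event | Opening clause (treatment period) | Branch | Result as written |
|---|---|---|---|
| New AE, Day 1 after dosing | met | not present at Baseline | TEAE |
| New AE, Days 2–14 | not met | not present at Baseline | not a TEAE, listing only |
| Present at Baseline, worsens Day 1 | met | worsening | TEAE |
| Present at Baseline, worsens Days 2–14 | doubtful | worsening, follow-up named | unclear: branch says yes, opening clause may say no |

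The last row shows that the sentence is also inconsistent with itself. The opening clause governs both branches, yet the second branch reaches into follow-up.

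**2. Share of assessments affected**

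The protocol synopsis gives "Assessment of safety (adverse events and PT/INR testing) Days 1, 2, 3, 7 and 14". Four of these five days fall in Follow-up. This is a share of assessment days, not of events; infusion reactions, for example, would still fall on Day 1.

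**3. Illustrative effect on the warfarin group (n = 25)**

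- Input: subjects with any AE in the pooled SOLO oritavancin arm, 540/976 = 0.5533 (Protocol Table 3; the AE window is not given there).
- Expected subjects with any AE: 25 × 0.5533 = 13.83.
- Let g be the assumed share of these subjects whose only new AEs start after Day 1. Tabulated subjects = 13.83 × (1 − g).

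| g (assumed) | Subjects in table | Tabulated rate | Subjects missing |
|---|---|---|---|
| 0 | 13.8 | 55.3% | 0 |
| 25% | 10.4 | 41.5% | 3.5 |
| 50% | 6.9 | 27.7% | 6.9 |
| 75% | 3.5 | 13.8% | 10.4 |

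**4. Chance of an uncommon event appearing in the table**

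Assume a 14-day risk of 5%. With the full window, the chance of at least one tabulated case in 25 is 1 − 0.95^25 = 72%. If half of the onsets are on Day 1, it is 1 − 0.975^25 = 47%.

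**5. Hypersensitivity timing**

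Protocol 1.2.4 gives a median onset of 1.2 days. If this is elapsed time from dosing (an assumption; no origin is stated), it is 1.2 × 24 = 28.8 h, so at least half of such reactions would start on Day 2 or later. If the dosing day is counted as Day 1, this does not follow.

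**6. A separate, smaller error in Protocol 8.3**

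The SAE reporting window there closes 14 days after the first *warfarin* dose, whereas Protocol 3.4, 8.2 and Table 1 and SAP 3.3 count from oritavancin. Warfarin subjects must have started at least 30 days before enrollment, so the window would close at least 30 − 14 = 16 days before enrollment. For the 15 non-warfarin subjects it is undefined. This concerns reporting to the sponsor and does not remove SAEs from the endpoint.

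**The case against.** The best case against is that nobody would program it this way. SAP 8.1 does not cite Protocol 6.4, its sentence mentions follow-up, and AEs are collected for 14 days as part of the primary endpoint. The likely intent is therefore the whole post-dose window. That reading of intent is fair, and the omission is a consequence of the text rather than a certainty. It does not rescue the wording: the sentence itself lists the treatment period and the follow-up period as two things, as Protocol 6 does, and extends only the worsening branch.

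It can also be said that the trial is small and descriptive, that no test or decision rule uses the TEAE count, and that every AE is listed by subject. All of this is true and limits the harm. The tables are still the stated summary of a primary-endpoint component, and readers will quote them rather than the listings.

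The counts above rest on assumed onset shares and on a rate from other trials. That stands too; the finding does not depend on them. Finally, the Protocol 8.3 error is a separate matter and adds no weight to this one.

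**Conclusion.** The rule is wrong as written. Taken with the protocol's own periods, it leaves new AEs on Days 2–14 out of the AE incidence tables, and it leaves open whether follow-up SAEs enter the SAE summary. It must be corrected before database lock. Confidence is high on the text. The size is not known: the tabulated rate could fall from 55.3% to anywhere between 41.5% and 13.8% under the assumed shares of 25% to 75%, if the SOLO rate applies. AE collection, by-subject listings, and the laboratory and vital-sign summaries are unaffected. The Protocol 8.3 wording is a minor item on its own.

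**What to change.** In SAP 8.1, define a TEAE as any AE with onset, or worsening from Baseline, at or after the start of the oritavancin infusion and through 14 days after administration. State that the SAE and discontinuation summaries use the same window. Because the last visit may be up to 2 days late, also say how an event starting after 14 days but recorded at that visit is shown, for example in the listing only.

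Make the same change in Protocol 10.3.3.1 so that the two documents agree. Separately, reconcile the SAE reporting window in Protocol 8.3 with the oritavancin-based window in Protocol 3.4, 8.2 and Table 1 and in SAP 3.3.

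The cost is one sentence in the SAP, the same sentence in the protocol, and one phrase in Protocol 8.3. No new data are needed. The protocol edits go through the IRB/EC as an amendment (Protocol 13.2). Protocol 10 leaves statistical detail to the SAP, so the SAP correction can be made first, before database lock.

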8.2 Clinical Laboratory Assessments

Clinical safety laboratory values and changes from baseline of hematology, serum chemistry, and urinalysis, including prothrombin time (PT)/international normalized ratio (INR), direct and indirect Coombs (DAT and IAT), Immunoglobulin panel, oritavancin antibody assay, will be summarized descriptively. Potentially clinically significant (PCS) values will also be flagged in a listing. The criteria for potentially clinical significant liver function tests are displayed in [Table 2](#).

Unscheduled assessments that are not used for baseline will not be included in summary tables; however, all measurements will be listed.

Table 2: Criteria for Potential Clinically Significant Abnormal Lab Tests

Parameter	Lower limit	Upper limit
Hematology		
Red Blood Cell Count	$\leq 0.75 \times \text{LLN}$	$\geq 1.25 \times \text{ULN}$
WBC's Count	$< 2.0 \times 10^9/\text{L}$	
Hematocrit	$\leq 0.75 \times \text{LLN}$	$\geq 1.25 \times \text{ULN}$
Hemoglobin	$\leq 11.5 \text{ g/dL}$ Male	$\geq 18.0 \text{ g/dL}$ Male
	$\leq 9.5 \text{ g/dL}$ Female	$\geq 16.0 \text{ g/dL}$ Female
Platelet count	$\leq 75 \times 10^9/\text{L}$	$\geq 700 \times 10^9/\text{L}$
Serum Chemistry		
BUN		$\geq 10.7 \text{ mmol/L}$
Calcium	$\leq 7.0 \text{ mg/dL}$	$\geq 15.5 \text{ mg/dL}$
Creatinine		$\geq 2.0 \text{ mg/dL}$
Glucose	$\leq 50 \text{ mg/dL}$	$\geq 180 \text{ mg/dL}$
Potassium	$\leq 3.0 \text{ mmol/L}$	$\geq 5.5 \text{ mmol/L}$
Sodium	$\leq 125 \text{ mmol/L}$	$\geq 150 \text{ mmol/L}$
Liver Function Tests (LFTs)		
Alanine Transaminase (ALT/SGPT) $\geq 3x, 5x, 10x$ and $20x \text{ ULN}$		
Aspartate Transaminase (AST/SGOT) $\geq 3x, 5x, 10x$ and $20x \text{ ULN}$		
ALT or AST $\geq 3x, 5x, 10x$, or $20x \text{ ULN}$		
Total bilirubin $\geq 1.5x$ and $2x \text{ ULN}$		
Alkaline Phosphatase (ALP) $\geq 1.5x$ and $3x \text{ ULN}$		
ALT/AST $\geq 3x \text{ ULN}$ and Total bilirubin $\geq 2x \text{ ULN}$;		
Potential Hy's Law cases: ALT or AST $\geq 3 \times \text{ULN}$, Total bilirubin $\geq 2 \times \text{ULN}$, and ALP $\leq 2 \times \text{ULN}$		

LLN: lower limit of the standard reference (normal) range.

ULN: upper limit of the standard reference (normal) range.

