#### 1.3. STUDY RATIONALE

As noted above, oritavancin is a weak inhibitor of CYP2C9 based on a 31% increase (90% confidence interval (CI) [1.294, 1.345]) in the systemic exposure of S warfarin (TMC-ORI-12-03). Two additional studies are ongoing; MDCO-ORI-14-01 is a Phase I study in healthy volunteers to assess the magnitude and duration of the effect of a single 1200 mg intravenous dose on numerous coagulation tests, including PT/INR, and MDCO-ORI-14-02 which is an additional Phase I study in healthy volunteers assessing the magnitude and duration of the pharmacokinetic (PK) interaction between warfarin and oritavancin. Since warfarin is a drug with a narrow therapeutic index and some patients with ABSSSI may receive oritavancin while on warfarin treatment, this study is being conducted to characterize the effect of oritavancin on clinical care and warfarin dosing. The intention is to determine the magnitude and duration, if any, of alterations to warfarin dosing or of clinically important consequences of dosing with oritavancin.

In the SOLO and SIMPLIFI trials, a total of 16 patients with ABSSSI received concomitant warfarin while treated with a single 1200 mg dose of oritavancin. Of these 16 patients, 10 were on warfarin prior to starting oritavancin, 4 received warfarin therapy after starting oritavancin therapy and for 2 patients the timing of warfarin therapy is unknown. None of these 16 patients discontinued from the study early due to adverse events. One patient experienced an event of infusion site thrombosis 2 days prior to the administration of warfarin therapy but there were no other bleeding or thrombotic related events. Additionally, no abnormal prothrombin time coagulation tests were reported in the oritavancin treated patients.

This study will extend the above safety data in patients with ABSSSI when oritavancin and warfarin are given concomitantly.

In addition, a group of patients with ABSSSI, who are not on concomitant warfarin therapy, have been added to this study to obtain information regarding the potential for antibody production following a single dose of oritavancin administration in patients. This has not been previously tested, therefore plasma will be collected at regular intervals after oritavancin dosing to test for immunoglobulins, direct and indirect Coombs, and presence of oritavancin antibodies.

The 1200 mg dose of oritavancin is the United States (US) approved therapeutic dose.

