## 3.3. MEASURES TO MINIMIZE/AVOID BIAS

# 3.3.1. Unblinded Study

This is an open label study. The primary endpoints are safety and laboratory measurements, primarily change in PT/INR, which is not likely to be subject to interpretation bias.

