## 5.2. CONCOMITANT MEDICATIONS

#### **5.2.1.** Prohibited Concomitant Medications

If possible, patients on chronic warfarin therapy should not take any new medications that could interfere with warfarin metabolism, other than oritavancin, during this study. Any concomitant medications will be recorded in the electronic case report form (eCRF) according to the Schedule of Events.

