#### **5.2.2.** Permitted Concomitant Medications

Subjects enrolled and treated with oritavancin may receive additional antibiotic therapy with gram-negative coverage if necessary.

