## **5.2.3.** Warfarin Therapy

Any changes in warfarin dosing (for patients on concomitant chronic warfarin), based on the PT/INR results or safety data will be captured.

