# 7.1.1. Medical management guidelines

Other interventions to optimize the care of subjects will be left to the discretion of the attending physician and investigator. These include surgical/nonsurgical debridement of devitalized tissue, removal of prosthetic material, incision and drainage, suture removal, percutaneous aspiration, packing, dressings, or irrigation with normal saline to remove superficial slough, excess exudate or visible debris. Standard of care therapy (such as daily superficial debridements and dressing changes) are allowed.

If a patient has an infusion reaction with oritavancin the infusion may be slowed or stopped. The patient should be treated as necessary. The infusion may be resumed at half the previous infusion rate with continued monitoring for signs or symptoms of a histamine infusion reaction.

If a patient is classified as a treatment failure by the investigator at any time, the patient may be administered alternative antibiotic therapy according to clinical judgment.

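### The planned PT/INR change summaries take no account of warfarin changes made in response to PT/INR, and no SAP table reports those changes

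*SAP*

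**What the plan says.** On the analysis, SAP 8.2 gives one descriptive treatment to all laboratory tests: "Clinical safety laboratory values and changes from baseline of hematology, serum chemistry, and urinalysis, including prothrombin time (PT)/international normalized ratio (INR" and the antibody tests. SAP section 4 groups data by cohort and by nothing else. Unscheduled results that do not serve as baseline are listed but kept out of the tables.

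On the weight of the measurement, Protocol 3.3.1 states: "The primary endpoints are safety and laboratory measurements, primarily change in PT/INR". Protocol 1.3 gives the study's intention as to "determine the magnitude and duration, if any, of alterations to warfarin dosing or of clinically important consequences" of oritavancin dosing.

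On what can happen to a subject between visits:
- Protocol 5.2.3: "Any changes in warfarin dosing (for patients on concomitant chronic warfarin), based on the PT/INR results or safety data will be captured".
- Protocol 5.2.1: "If possible, patients on chronic warfarin therapy should not take any new medications that could interfere with warfarin metabolism, other than oritavancin".
- Protocol 5.2.2: subjects "may receive additional antibiotic therapy with gram-negative coverage if necessary".
- Protocol 7.1.1, after treatment failure: "the patient may be administered alternative antibiotic therapy according to clinical judgment".

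**The concern.** The measurement that Protocol 3.3.1 puts first is also the trigger for an intervention that moves it. A subject whose INR rises after oritavancin may have warfarin changed, and the next scheduled INR then reflects both oritavancin and the change. SAP 8.2 averages that value with values from subjects whose warfarin was untouched.

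A mean change near zero at Day 7 or Day 14 then has two explanations: the effect is over, or it continues and a warfarin change offsets it. The summary cannot choose between them, and no concurrent group helps. Subjects not on warfarin cannot show what INR would have been in a warfarin subject left unadjusted.

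The second half of the problem is that the changes themselves go unreported. Their magnitude and duration are what Protocol 1.3 sets out to determine, yet the SAP has no table for them.

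**Working it through.** **Does anything in the SAP separate or report the affected values?**
- *Missing data (5.3).* Only missing values are excluded. An INR taken after a warfarin change is not missing, so it stays in.
- *Medication summary (6.3).* Each subject counts once per medication and period, so a change of warfarin dose does not show. A drug with a partial date is classed as prior, which could hide a post-dose start.
- *Abnormal-value criteria (Table 2).* There is no PT/INR threshold, so no out-of-range flag is defined.
- *Extra PT/INR tests.* Footnote 7 of the schedule foresees more frequent testing between Day 3 and Day 7. These results are unscheduled and so are left out of the tables.
- *Exploratory analysis (section 10).* None is planned.
- *Listings.* Laboratory values and medications are listed by subject.

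So the tables neither separate nor report; only the listings hold the information.

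**Is a residual effect at Day 7 or Day 14 plausible?** Protocol Table 2 gives a terminal half-life of 245 h, AUC0-72 of 1530 and AUC0-∞ of 2800 µg·h/mL.
- Terminal-phase component relative to its time-zero value, 2^(−t/245): 0.665 at 144 h and 0.622 at 168 h (about Day 7); 0.414 at 312 h and 0.387 at 336 h (about Day 14).
- Share of exposure after 72 h: 1 − 1530/2800 = 45%.

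Continued exposure does not prove a continued INR effect, but it means one cannot be ruled out in advance.

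**How large could the attenuation be?** The plan gives no figure to reproduce: no adjustment rate, expected INR shift or SD. Take n = 25 (SAP 3.1) and assume that every subject has the same persistent shift δ and that k subjects have been brought back to baseline. The mean change is (1 − k/25)δ, so the attenuation is k/25 whatever δ is. With δ = 0.5 assumed:

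| k | mean change | attenuation |
|---|---|---|
| 3 | 0.44 | 12% |
| 5 | 0.40 | 20% |
| 8 | 0.34 | 32% |

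An error in the other direction is also possible. If no effect remains but an earlier change still lowers INR by 0.5 in k subjects, the mean is −0.5k/25 = −0.06, −0.10 and −0.16 for the same k.

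The binomial chance of at least 3 adjusted subjects among 25 is 13%, 46%, 90% or 99% at assumed adjustment rates of 5%, 10%, 20% or 30%.

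**Would a mean of pre-change values only solve it?** Assume instead that k subjects go from INR 2.4 to 3.6 at Day 3, have warfarin changed and are back at 2.4 by Day 7, with the others unmoved. The Day 3 mean change is 1.2k/25 = 0.14, 0.24 and 0.38 for k = 3, 5 and 8. At Day 7 the all-subject mean is 0.00. The pre-change mean, over the remaining 25 − k, is also 0.00 for every k, because it drops exactly the subjects who were affected. It recovers δ only if every subject has the same shift.

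**The case against.** The strongest reply is that INR as observed under usual care is a proper safety summary for a study of clinical care and warfarin dosing. That stands, and the all-subject summary should remain primary.

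A reader might infer that Protocol 1.3 asks how long the INR effect lasts and that the plan fails that aim. It does not say so. Its magnitude-and-duration wording concerns warfarin dosing and clinically important consequences. The same section points to Phase I studies in healthy volunteers for the coagulation effect (MDCO-ORI-14-01) and the pharmacokinetic interaction (MDCO-ORI-14-02). This narrows the point on INR but sharpens the one on dose changes, which are the stated aim and have no table.

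A reader might also infer that the Day 7 and Day 14 results are uninterpretable. That is too strong. With about 25 subjects the listings can be read individually, and medians and quartiles are planned. In the uniform-shift example the median stays at δ until 13 of 25 are brought back. But a reconstruction devised after database lock would be labelled post hoc under SAP section 4.

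Nor do the documents say that the permitted antibiotics interact with warfarin. Protocol 5.2.1 speaks only of new drugs that could, and Protocol 4.3 excludes suspected or documented Gram-negative infections, which limits the need for added cover. That part is conditional; the point on warfarin changes does not need it.

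Finally, Protocol 1.3 reports no abnormal prothrombin time tests in the oritavancin-treated patients of earlier trials, 16 of whom received warfarin, 10 of them before oritavancin. This is thin evidence, but it gives no support for assuming frequent large shifts.

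**Conclusion.** The point holds for the planned tables. SAP 8.2 summarises PT/INR change by cohort without regard to warfarin changes that the same results may trigger, and no SAP table reports those changes. The Day 7 and Day 14 summaries can be attenuated towards zero and cannot, on their own, distinguish an ended effect from one offset by a warfarin change.

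The size is unknown. The 12% to 32% range rests on a uniform persistent shift in all 25 subjects and on 3 to 8 of them returning to baseline, neither of which comes from the documents. This is a gap in presentation that is cheap to close before database lock; it does not invalidate the PT/INR data.

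**What to change.** In SAP 8.2, for the warfarin cohort, keep the all-subject PT/INR summary as primary and add:

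1. At each visit, the number and percentage of subjects with INR outside 1.5 to 3.0 at that visit or any captured post-dose warfarin change up to it, with the two components also shown separately. The band is the eligibility range of Protocol 4.2, used only as a descriptive reference. Eligible warfarin subjects all start inside it. Count any captured change, because Protocol 5.2.3 does not say that PT/INR-based and other safety-based reasons are recorded apart.
2. At each visit, PT/INR change side by side for subjects with and without a prior post-dose warfarin change, with n. In the listing, flag values obtained after the start of a drug that could interfere with warfarin metabolism, and mark drugs with partial dates.
3. A table of the number, timing, direction, size and duration of warfarin changes, which serves Protocol 1.3 directly.

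State that a mean of pre-change values only will not be used as evidence that the effect has ended, because removing subjects for a high INR biases it towards no effect.

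Cost: SAP wording, a few table rows, a review of concomitant drugs, and a check that the eCRF holds dates and doses for warfarin changes. No visits or samples are added. Limits: the side-by-side groups will be small, selected on outcome and descriptive only. The combined count in item 1 cannot be masked by an adjustment, but it is partly cumulative and so does not itself show when an effect ends; the separate components and the table in item 3 inform that.
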